## 2. SUMMARY OF CLINICAL EXPERIENCE

The clinical experience with olaparib is fully described in the current version of the olaparib Investigator's Brochure.

The first clinical study in man (D0810C00002) was a dose-escalation study in patients with advanced solid tumours. A total of 98 patients were recruited and doses started from 10 mg daily for 2 or 3 weeks, escalating to 600 mg bid continuously. After the maximum tolerated dose was identified (400 mg bid), an expansion phase at 200 mg bid was opened in ovarian, breast and prostate cancer patients who have genetic BRCA mutations.

Of the 98 patients treated across all tumour types, 49 had ovarian cancer and were BRCA mutation carriers as defined by a molecular test. One additional patient had not had a molecular test, but had a compelling family history and considered likely to be a BRCA mutation carrier. A further 4 patients with ovarian cancer were not BRCA mutation carriers.

All 49 ovarian cancer patients with genetic BRCA mutations had received prior platinum chemotherapy. In this study there were 12 (24.5%) confirmed responses per RECIST for this group. Five of the confirmed responders (4 at 200 mg bid and 1 at 400 mg bid dose level) were patients who were sensitive to platinum (38.5% ORR; 5/13 platinum sensitive patients), and 7 confirmed responders (5 at 200 mg bid and 2 at 400 mg bid dose level) were patients categorised as resistant to platinum (30.4% ORR; 7/23 platinum resistant patients).

Using the combined GCIG/RECIST criteria, 18 patients (36.7%) had a confirmed response. Responses were seen in 7 of 13 sensitive patients (53.8%), 9 of 23 resistant patients (39.1%) and 2 of 13 refractory patients (15.4%). The higher response rates observed in the platinum sensitive subgroup and lower response rate observed in the platinum refractory subgroup is consistent with the response rates seen using RECIST only, and time to disease progression.

Responses were seen at all dose levels of 100 mg bid and above.

Safety data from this study indicate that oral administration of olaparib was generally well tolerated by the majority of patients with various solid tumours at doses up to and including 400 mg twice daily, as monotherapy, although, as expected, all patients on olaparib experienced at least one adverse event. Most of the AEs were mild to moderate (CTCAE grade 1 or 2) in intensity at doses up to 400 mg bid. Dose Limiting Toxicity (DLT) was observed at 600 mg bid. The percentage of patients with CTCAE grade  $\geq 3$  events attributed to the study medication by the Investigator was 23.5% (23 patients), and increased with increasing dose. The percentage of patients with AEs leading to discontinuation of treatment was 21.4% (21 patients), with only 5.1% (5 patients) discontinuing treatment due to events that the Investigator attributed to study drug. There were only 4 dose reductions for adverse events in the entire population of 98 patients treated; all were at the 200 to 600 mg bid dose levels.

Study D0810C0009 is a Phase II open-label, non-comparative study to assess the efficacy and safety of olaparib given orally twice daily in ovarian cancer patients with genetic BRCA-1 or BRCA-2 mutations. A total of 57 patients were recruited into two separate sequential cohorts, the first treated at a dose of 400 mg bid and the second by a dose of 100 mg bid. Olaparib dosing was continuous and continued until there was no apparent clinical benefit or the patient was withdrawn from the study.

The objective response rate observed in both dose groups is indicative that olaparib is an active agent in this heavily treated population who had received a median of 3 previous lines of chemotherapy (35.5% at 400 mg bid and 13.6% at 100 mg bid). In this non-randomised study a higher level of activity was observed across all parameters in the 400 mg bid group compared to the 100 mg bid group (ORR, DoR (mean of 242.0 days at 100 mg bid and 301.0 days at 400 mg bid), CBR (45.5% at 100 mg bid and 71.0% at 400 mg bid), PFS (2.1 mths at 100mg bid and 7.4 mths at 400 mg bid) and best % change in tumour size [mean of -6.4% at 100 mg bid and -32.1% at 400 mg bid]). Confirmed objective responses were seen in patients with both BRCA1 and BRCA2 mutations.

As expected in patients with advanced cancer, most of the patients (98.2%) experienced at least one adverse event. In total, 49 patients (86.0%) experienced at least one adverse event that the Investigator attributed to study medication. AEs occurring in  $\geq 25\%$  of patients across the two dose cohorts were nausea (36 patients, 63.2%), fatigue (30 patients, 52.6%), diarrhoea (19 patients, 33.3%), abdominal pain (including “lower abdominal pain” and “upper abdominal pain”, 18 patients, 31.6%), and vomiting (17 patients, 29.8%). A total of 31 patients (54.4%) had at least 1 AE of CTC grade  $\geq 3$ ; 14 patients in the 100 mg bid group and 17 patients in the 400 mg bid group. The number of patients with CTC grade  $\geq 3$  events that the Investigator considered related to olaparib was 24.6% (14 patients overall, 7 in each treatment group). Most of the AEs were mild to moderate in intensity and manageable with continued dosing of olaparib. There were few dose interruptions and reductions required due to toxicity and only 5 patients had to discontinue olaparib due to AEs.

Overall results across the clinical trial program to date suggest that olaparib (in the capsule formulation) appears to be generally well tolerated in patients with various solid tumours at doses up to and including 400 mg twice daily, as monotherapy.

### **Olaparib toxicity**

Administration of olaparib has been associated with reports of laboratory findings and/or clinical diagnoses of:

- Haematological toxicity:
  - Anaemia, generally mild or moderate (CTCAE Grade 1 or 2)
  - Neutropenia, predominantly mild or moderate (CTCAE Grade 1 or 2)
  - Lymphopenia, generally mild or moderate (CTCAE Grade 1 or 2)

- Thrombocytopenia, generally mild or moderate (CTCAE Grade 1 or 2) sometimes severe (CTCAE Grade 3 or 4)
- Mean corpuscular volume elevation
- Nausea and vomiting, generally mild or moderate (CTCAE Grade 1 or 2), intermittent and manageable on continued treatment
- Dyspepsia, generally mild or moderate intensity (CTCAE Grade 1 or 2)
- Dysgeusia, generally mild or moderate intensity (CTCAE Grade 1 or 2)
- Fatigue (including asthenia) generally mild or moderate intensity (CTCAE Grade 1 or 2)
- Headache, generally mild or moderate intensity (CTCAE Grade 1 or 2)
- Dizziness, generally mild or moderate intensity (CTCAE Grade 1 or 2)
- Pneumonitis events with no consistent clinical pattern have been reported in a small number of patients
- Myelodysplastic syndrome/AML have been reported in a small number of patients with extensive previous exposure to chemotherapy

### **Cisplatin toxicity**

Cisplatin has been used in combination regimens in the treatment of several malignancies including testes, head and neck (squamous carcinomas), and lung cancers. A summary of characteristic toxicities includes: [\(Go and Adjei 1999\)](#).

- **Nephrotoxicity**

The major dose-limiting toxicity of cisplatin is cumulative nephrotoxicity. Tubular necrosis of both proximal and distal renal tubules has been noted in 28% to 36% of patients treated with a single dose of 50 mg/m^2. It is first noted during the second week after a dose and is manifested by elevations in BUN and creatinine, serum uric acid and/or a decrease in creatinine clearance. Renal toxicity becomes more prolonged and severe with repeated courses of the drug. Renal function must return to normal before another dose of cisplatin can be given. Nephrotoxicity can be reduced by IV hydration and mannitol diuresis.

- **Nausea and Vomiting**

Cisplatin causes moderate to severe nausea and vomiting in almost all patients treated. Nausea and vomiting usually begin within 1 to 4 hours after treatment and last up to 24 hours. Various degrees of vomiting, nausea, and/or anorexia may persist for up to 1 week after the treatment. Delayed nausea and vomiting (beginning 24 hours or more after chemotherapy) has occurred

with complete emetic control on the day of cisplatin therapy. The use of prophylactic and continuing antiemetic medication reduces these adverse effects.

- **Hypomagnesemia**

Hypomagnesaemia have been reported in patients treated with cisplatin and is probably related to renal tubular damage. It may become severe enough to cause tetany. Generally, serum electrolytes return to normal levels when cisplatin is discontinued and supplemental electrolytes are administered.

- **Ototoxicity**

Ototoxicity has been observed in up to 31% of patients treated with a single dose of cisplatin (50 mg/m^2) and is manifested by tinnitus and/or hearing loss in the high frequency range (4000 to 8000 Hz). Decreased ability to hear normal conversational tones may occur occasionally. Ototoxicity can be more severe in children than in adults and more frequent and severe with repeated administration. Hearing loss can be unilateral or bilateral and is usually not reversible. During treatment with cisplatin, it is necessary to monitor hearing at each visit. An audiogram is recommended after a cumulative dose of 360 mg/m^2. Subsequent doses of cisplatin should not be given until an audiometric analysis indicates that auditory acuity is within normal limits.

- **Myelosuppression**

Myelosuppression occurs in 25% to 30% of patients treated with cisplatin. The nadirs in circulating platelets and leukocytes occur between days 18 and 23, with most patients recovering by day 39. Leukopenia and thrombocytopenia are more pronounced at higher doses (>50 mg/m^2). Anemia (a decrease in hemoglobin of 2 g/100 ml) occurs at approximately the same frequency and with the same timing as leukopenia and thrombocytopenia.

- **Neurotoxicity**

Cisplatin neurotoxicity is characterized by peripheral neuropathies, which are sensory in nature but can also include motor difficulties such as reduced deep-tendon reflexes and leg weakness. The symptoms usually occur after prolonged therapy (4 to 7 months). Cisplatin therapy should be discontinued when serious neuropathy develops. The neuropathy, however, may progress further even after discontinuation of treatment.

In the DF/HCC neoadjuvant trial of 4 cycles of cisplatin 75mg/m^2 q21 days in 28 women with triple negative breast cancer, only one grade 4 toxicity was observed, an elevation in SGOT. There were 7 grade 3 symptomatic toxicities: one each, fatigue, abdominal pain, GI toxicity unspecified, myalgias, skin toxicity and tinnitus. Grade 3 toxicities in laboratory tests were seen in 2 women with low white blood cells and one each hyperkalemia and elevation in SGPT.

## **2.1 Rationale**

### **2.1.1 Combination therapy of PARP-1 inhibitors with cisplatin in advanced solid tumours**

Cisplatin interferes with the growth of cancer cells, slowing their advance in the body.

Cisplatin is currently approved by the Food and Drug Administration (FDA) to be used by itself to treat the following conditions:

- Bladder Cancer that cannot be treated with surgery or radiotherapy.
- Ovarian cancer that has metastasized (spread to other parts of the body) and has not gotten better with other drugs.

Cisplatin is approved to be used together with other drugs to treat the following conditions:

- Advanced ovarian cancer in patients who have already had surgery.
- Metastatic ovarian cancer in patients who have already had surgery or radiotherapy.
- Testicular cancer in patients who have already had surgery or radiotherapy.
- Locally advanced squamous cell carcinoma of the head and neck (SCCHN) that cannot be treated with surgery.
- Late-stage cervical cancer that cannot be treated with surgery or radiotherapy.
- Malignant mesothelioma that cannot be treated with surgery.
- Locally advanced, advanced, or metastatic non-small cell lung cancer (NSCLC) that cannot be treated with surgery.

In addition to the approved indications by the FDA, cisplatin is also used alone or with other drugs to treat other types of cancer. Cisplatin continues to be studied in the treatment of many types of cancer.

Breast cancer is the most commonly diagnosed cancer and the second leading cause of cancer deaths after lung cancer in American women. In modern oncology, it is increasingly possible to recognize subsets of common cancers, and to target therapies based on particular features of specific subsets. In breast cancer, therapies targeting the oestrogen receptor (ER) are effective only in tumours expressing ER. The antibody therapy, trastuzumab, has shown remarkable efficacy against tumours shown to have amplified or overexpressed HER2 genes. The amplification of HER2 is an acquired event in tumour cells only.

Recent data from cell lines suggests that breast cancers arising in patients with BRCA1 mutations may be more sensitive to the cidal effects of cisplatin than other breast cancers ([Bhattacharyya et al 2000](#), [Moynahan et al 2001](#), [Husain et al 1998](#), [Tassone et al 2003](#),

Quinn et al 2003). Accumulating data suggest that specific alterations in genes in the BRCA1 double strand break repair pathway may result in tumours that are less capable of repairing specific types of DNA errors. In addition, most BRCA1-associated cancers have been shown to be poorly differentiated, ER/PR negative, HER2 negative, and to belong to the basal-like subset of tumours as characterized in tissue microarrays (Sorlie et al 2003, Lakhani et al 2002). These basal-like tumours show high expression of proliferation-associated genes and over-expression of genes that are normally expressed in myoepithelial or basal cells of normal breast tissue such as the basal keratins and smooth muscle actin; hence the name, "basal-like" or "basaloid" (Sorlie et al 2003). Moreover, the "basaloid" tumours not associated with germline BRCA1 mutations are also typically lacking ER/PR receptors, are histologically high grade, and are reported to be positive for basal-like keratins. In fact, basaloid tumours appear to comprise 80% of ER/PR/HER2 negative breast cancers. Since the precise mechanism of the increased cisplatin sensitivity of the BRCA1-associated basaloid tumours is unknown, it is possible that it is maintained in the basaloid tumours not associated with germline BRCA1 mutations. In BRCA2 deficient mammary cell lines, tumor cells were demonstrated to be exquisitely sensitive to PARP inhibition with AZD2281 alone or, as a result of potent synergy, in combination with cisplatin (Evers et al 2008).

Agents that inhibit PARP have the potential to improve the therapeutic efficacy of several commonly used chemotherapeutics in oncology.

Previous ongoing studies to date with AZD2281 have demonstrated inhibition of PARP over a range of doses with evidence of clinical efficacy and an acceptable safety and tolerability profile.

The study is designed to provide a tolerated dose of AZD2281 combined with cisplatin which can be investigated in further studies.

### **3. STUDY OBJECTIVES**

#### **3.1 Primary objective**

- The primary objective is to determine the safety and tolerability of twice daily oral doses of AZD2281 when administered in combination with cisplatin to patients with advanced solid tumours.

#### **3.2 Secondary objectives**

The secondary objectives of the study are:

- To compare exposure to AZD2281 when given alone and in combination with cisplatin. (Only in patients receiving continuous dosing of AZD2281)
- To make a preliminary assessment of the anti-tumour activity of AZD2281 when given in combination with cisplatin, by measuring overall response rate.

### 3.3 Exploratory objectives

- To obtain an optional blood sample for DNA extraction for future pharmacogenetic analysis and other potential correlative markers of the activity of AZD2281 and drugs taken in combination with AZD2281 (i.e. cisplatin).

The exploratory analyses will be reported separately.

## 4. STUDY PLAN AND PROCEDURES

This Clinical Study Protocol has been subject to a peer review according to AstraZeneca standard procedures.

### 4.1 Overall study design

The study is a Phase I non-randomised, open label, dose finding study, to determine the maximum tolerated dose of AZD2281 that can be combined with cisplatin in patients with advanced solid tumours.

Each cohort will comprise a minimum of 3 evaluable patients. If 1 patient from the initial 3 experiences DLT the cohort will be expanded to at least 6 patients. It is expected that 60 patients will be enrolled.

Once the desired dose or MTD of the combination therapy has been determined (or the highest dose level has been explored) the cohort will be expanded to ensure that there are 6 evaluable patients who have completed four cycles of treatment.

If continuous dosing is not tolerated, intermittent dosing will be explored. An intermittent dosing cohort will be opened to enrol 12 patients at the following dose:

- AZD2281 at 100 mg bid for days 1-10 of a 21 day cycle with 75 mg/m^2 of cisplatin on day 1 of a 21 day cycle
- Day 1 of cisplatin and day 1 of AZD2281 are the same day

In the event that the first intermittent dose cohort is not tolerated, further cohorts may be investigated with a starting dose of AZD2281 at 50 mg bid for days 1-5 of a 21 day cycle with 75 mg/m^2 of cisplatin.

Further cohorts may be considered following review by the safety monitoring committee. The cohort options to be considered are described in [Table 3](#).

For the continuous dosing regimens, at visit 2, study day 1 (+3 days), only a morning dose of AZD2281 will be administered. On the morning of study day 1, patients will attend the clinic to begin cycle 0 where, in addition to receiving a cohort-specific oral dose of AZD2281, samples for a full 12-hour plasma PK profile will be taken. From Cycle 1 at visit 3 Study day

8 and on each day thereafter, AZD2281 will be taken orally twice-daily. Also on day 8, cisplatin will be administered 2 hours after AZD2281 administration. This will be day 1 of the 21-day cycle. A full 12-hour plasma PK profile will also be repeated at this visit to enable a comparison of AZD2281 PK when given alone and in combination with cisplatin. Pharmacokinetic (PK) blood samples will be collected for patients receiving continuous dosing of AZD2281 as described in Section 5.3.

For the intermittent dosing regimens, the first AZD2281 administration will be on the same day as cisplatin administration, unless a different dose schedule is advised by the safety monitoring committee. PK blood draws will not be performed for patients enrolled into an intermittent dosing cohort.

The Maximum Tolerated Dose (MTD) is defined as the prior dose level below the drug-combination that causes DLT, in at least 2 patients in a cohort of up to 6 patients. If toxicity is equivocal and it is not possible to determine a DLT with certainty, further cohorts of three patients will be recruited to allow an informed decision to be taken about further dose escalations with AZD2281.

The dose escalation will continue until the MTD is established, however the highest dose to be explored will be 400 mg bid. Intra-patient dose escalation is not permitted.

#### **4.1.1 Stopping criteria for dose escalation**

AZD2281 will commence at 50 mg twice-daily in cohort 1, then increase to 100 mg twice-daily and 200 mg twice-daily. A further dose-escalation of AZD2281 to 400 mg twice-daily may be considered following review of the data. The dose of cisplatin will be 75 mg/m^2.

Dose-escalation of AZD2281 will stop if Dose Limiting Toxicity of the drug-combination occurs. At least three patients treated in a cohort must undergo repeated safety evaluations, up to and including Day 21, before enrolment of patients in the next dose cohort begins. Decisions to escalate to the next level, or, when appropriate, to an intermittent level, will be made jointly by the investigator and sponsor's Responsible Medical Officer based on review of all the available data.

If one patient in a cohort of 3 evaluable patients experiences a dose-limiting toxicity (DLT) during the first cycle that is considered related to combination-therapy, the cohort will be expanded to at least 6 patients.

In the continuous dosing schedule, Pharmacokinetic (PK) evaluations will be performed and may be utilised to guide appropriate changes to the regimen, if indicated. Cisplatin has the potential to cause nephrotoxicity which may affect clearance of other agents, including AZD2281.

Table 2 shows the continuous dosing escalation strategy to be adopted:

**Table 2** Proposed dose escalation schedule for the continuous dosing regimens

Cohort	Number of patients recruited	Cisplatin dose Q21d	AZD2281 dose	Schedule
1	3 – 6	75 mg/m 	50 mg bid	Continuous
2	3 – 6	75 mg/m 	100 mg bid	Continuous
3	3 – 6	75 mg/m 	200 mg bid	Continuous

In the event that the continuous dosing regimens are not tolerated, intermittent dosing regimens will be explored.

Table 3 shows the intermittent dosing strategy to be adopted:

**Table 3** Proposed dose schedule for the intermittent dosing regimens

Cohort	Number of patients recruited	Cisplatin dose Q21d	AZD2281 dose	Schedule
4	12	75 mg/m 	100 mg bid	Day 1-10 of the 21-day cycle
5	4-12	75 mg/m 	50 mg bid	Day 1-5 of the 21-day cycle
	4-12	75 mg/m 	50 mg bid	Day 1-3 of the 21-day cycle
	4-12	60 mg/m 	50 mg bid	Day 1-5 of the 21-day cycle
	4-12	75 mg/m 	50 mg bid	Day 2-6 of the 21-day cycle
	4-12	75 mg/m 	100 mg bid	Day 1-5 of the 21-day cycle

Further cohorts may be considered following review by the safety monitoring committee. The cohort options below will be considered.

The following additional points concerning the dose escalation strategy should be noted;

- Either agent may be dose-reduced, although only one agent should be modified at a time.
- No intra-patient dose-escalation will be permitted (whilst the patient is on combination therapy).
- A minimum of 3 patients per cohort must be treated, followed up and assessed for 21 days prior to recruiting patients into subsequent cohorts.
- Once the desired dose or MTD of the combination therapy has been determined (or the highest dose level has been explored) the cohort will be expanded to a to ensure that there are 6 evaluable patients who have completed four cycles of treatment.
- In the event that cisplatin is permanently discontinued on the basis of cisplatin related toxicity, treatment with AZD2281 alone may continue. If the patient does continue on AZD2281 alone, at the discretion of the PI and in consultation with AstraZeneca Study Team Physician, the patient may be dose escalated to receive the optimal monotherapy dose (ie: 400 mg bid).

A patient will be defined as evaluable for assessment of safety and tolerability for AZD2281 in combination with cisplatin if they:

- Complete at least 1 cycle of cisplatin (3 weeks) and also receives at least 75% of the planned continuous or intermittent dosing of AZD2281.

OR

- Experience DLT on combination treatment prior to fulfilling the above criteria.

Patients on the continuous dosing schedules are evaluable for PK evaluation if they are able to provide a full AZD2281 PK profile collected both with and without cisplatin.

#### **4.1.2 Dose Limiting Toxicity**

Toxicity will be graded using the NCI Common Terminology Criteria for Adverse Events (NCI CTCAE) Version 3.0. Dose-limiting toxicity (DLT) is defined as the following study drug-related events experienced during Cycle 1:

- Grade 4 thrombocytopenia.
- Grade 4 neutropenia lasting >5 days.
- Febrile neutropenia (ANC <1.0 x10^9/L with fever ≥38.5°C).
- Treatment delay of >2 weeks.

- Other Grade 3 non-haematological toxicities; excluding non-optimally treated nausea, vomiting and diarrhea

Patients with dose-limiting toxicity after cycle 1 who have documented clinical benefit (stable disease or an objective response) may continue to be treated at a reduced dose level if considered clinically appropriate by the investigator.

Any patient in whom a DLT occurs during any cycle will have his or her treatment delayed until toxicity resolves to grade 1 or below.

[figure not shown]

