#### 4.5.3.6 Management of Non-Hematologic NCI-CTCAE grade 3 or 4 AZD2281 Treatment Related Adverse Events

Treatment with AZD2281 must be interrupted for any non-hematologic CTCAE grade 3 or 4 adverse event which the Investigator considers to be related to administration of AZD2281. Repeated dose interruptions of up to a maximum of 28 days are allowed. Patients whose NCI CTCAE grade 3 or 4 event does not resolve to  $\leq$  grade 1 or to the baseline CTCAE grade after a full 28 day dose interruption should be withdrawn from the study.

Upon appropriate resolution of the toxicity (i.e., to NCI CTCAE grade 1 or to baseline CTCAE grade), the patient should restart treatment with AZD2281 but with a 50% dose reduction (as per [Table 7](#)). The dose of AZD2281 should not be reduced to less than 50 mg bid daily for patients receiving continuous AZD2281 dosing or to less than 50 mg bd for days 1-3 of a 21 day cycle for patients receiving intermittent AZD2281 dosing.

If the event recurs with the same severity, treatment should be interrupted again and, on resolution, a further dose reduction made where allowed.

Once a chemotherapy combination dose is reduced due to toxicity, combined chemotherapy dose re-escalation is not permitted.

**Table 7 Management of Non-Hematologica Grade 3 and 4 AZD2281 Treatment Related Adverse Events whilst the patient is receiving combination therapy**

Initial Dose Level c	1 st Event Occurrence - Recommended Dose Reduction	2 nd Event Occurrence – Recommended Dose Reduction	Dose Administration
100 mg bid	50 mg bid	No reduction allowed – withdraw patient	Continuous
200 mg bid	100 mg bid	50 mg bid	Continuous
400 b mg bid	200 mg bid	100 mg bid	Continuous
50 mg bid	No reduction allowed – withdraw patient	Not applicable	Continuous

**Table 7 Management of Non-Hematologica Grade 3 and 4 AZD2281 Treatment Related Adverse Events whilst the patient is receiving combination therapy**

Initial Dose Levelc	1st Event Occurrence - Recommended Dose Reduction	2nd Event Occurrence – Recommended Dose Reduction	Dose Administration
100 mg bid days 1-10 of a 21 day cycle	100 mg bid days 1-5 of a 21 day cycle	100 mg bid days 1-3 of a 21 day cycle	Intermittent
50 mg bid days 1-5 of a 21 day cycle	50 mg bid days 1-3 of a 21 day cycle	50 mg bid days 1-3 of a 21 day cycle Reduce cisplatin to 60 mg/m 	Intermittent

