## **Variables**

The following variables will be collect for each AE;

- AE (verbatim)
- The date when the AE started and stopped
- Changes in NCI CTCAE grade and the maximum CTC grade attained
- Whether the AE is serious or not
- Investigator causality rating against the Investigational Product (yes or no), comparator/combination drug (yes/no)
- Action taken with regard to investigational product/combination agent
- Outcome.

In addition, the following variables will be collected for SAEs:

- Date AE met criteria for serious AE
- Date Investigator became aware of serious AE
- AE is serious due to
- Date of hospitalisation
- Date of discharge
- Probable cause of death
- Date of death
- Autopsy performed
- Description of AE
- Causality assessment in relation to Study procedure(s)
- Causality assessment in relation to Other medication
- Causality assessment in relation to Additional Study Drug

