## **Adverse Events based on examinations and tests**

The results from protocol mandated laboratory tests and vital signs will be summarised in the clinical study report. Deterioration as compared to baseline in protocol-mandated laboratory

values, vital signs should therefore only be reported as AEs if they fulfil any of the SAE criteria or are the reason for discontinuation of treatment with the investigational product and combination drug.

If deterioration in a laboratory value/vital sign/ECG is associated with clinical signs and symptoms, the sign or symptom will be reported as an AE and the associated laboratory result/vital sign/ECG will be considered as additional information. Wherever possible the reporting Investigator uses the clinical, rather than the laboratory term (e.g., anaemia versus low haemoglobin value). In the absence of clinical signs or symptoms, clinically relevant deteriorations in non-mandated parameters should be reported as AE(s).

Deterioration of a laboratory value, which is unequivocally due to disease progression, should not be reported as an AE/SAE

Any new or aggravated clinically relevant abnormal medical finding at a physical examination as compared with the baseline assessment will be reported as an AE.

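### The DLT list names only Grade 3 for other non-haematological toxicity, so read literally a related Grade 4 or fatal event in Cycle 1 can drop out of the count that sets the MTD

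*Protocol*

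**What the plan says.** Section 4.1.2 opens its definition with "Dose-limiting toxicity (DLT) is defined as the following study drug-related events experienced during Cycle 1" and lists five items. Three are haematological: "Grade 4 thrombocytopenia", "Grade 4 neutropenia lasting >5 days" and febrile neutropenia. The fourth is "Treatment delay of >2 weeks". The fifth is "Other Grade 3 non-haematological toxicities; excluding non-optimally treated nausea, vomiting and diarrhea".

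Elsewhere the protocol grades non-haematological toxicity with an open or higher upper end:

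- Section 4.5.3.6: "Treatment with AZD2281 must be interrupted for any non-hematologic CTCAE grade 3 or 4 adverse event" if the investigator considers it related to AZD2281.
- Section 4.4.6.1 (discontinuation criteria) refers to Grade 3 or 4 events.
- Section 4.5.3.8 and Table 8 use Grade 3 and above for neurotoxicity and for other clinically significant toxicities, and deal separately with Grade 4 toxicity attributed to cisplatin.

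Two sections decide what happens to the patient in the count. Under Section 4.1.1 a patient is evaluable after completing a cycle with at least 75% of planned AZD2281, or after a DLT. Under Section 4.1.3 a patient who does not complete Cycle 1 for a reason other than DLT is unevaluable for the MTD and may be replaced, although still included in the evaluation of toxicity and efficacy.

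On attribution, Section 5.10.3 lists "Investigator causality rating against the Investigational Product (yes or no), comparator/combination drug (yes/no") among the variables collected for each adverse event (AE). For worsening results of scheduled laboratory tests it also sets a limit: "values, vital signs should therefore only be reported as AEs if they fulfil any of the SAE criteria". The same sentence allows one other ground, namely that the finding caused treatment to be stopped.

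**The concern.** The DLT definition decides whether a cohort is expanded, which patients are evaluable, who may be replaced, and where the MTD lies. With a threshold of two patients with DLT, a single uncounted event can change a cohort's outcome. Where the protocol means an open upper end it says so, so the bare Grade 3 in Section 4.1.2 conflicts with its other sections. The effect runs the wrong way: a Grade 3 event counts against the dose, while a more severe event of the same kind may not.

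The second, smaller issue is that a DLT must be drug-related, yet the only stated place for an investigator's causality rating is the AE record. Some laboratory findings that meet a DLT criterion need not become AEs.

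**Working it through.** **Reading the rule through for one case.** Take a related Grade 4 neurotoxicity in Cycle 1.

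1. Section 4.1.2: it is not haematological and not Grade 3, so it can be a DLT only through the treatment-delay item.
2. Section 4.5.3.8 and Table 8: both drugs are stopped and the patient leaves the study. There is no delayed treatment for the delay item to catch.
3. Section 4.1.1: the cycle is not completed and no listed DLT has occurred, so the patient is not evaluable.
4. Section 4.1.3: the patient is unevaluable for the MTD and may be replaced. Section 7.4.5 adds patients until at least three are evaluable.

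A fatal related non-haematological event follows the same path. If instead the patient completes the cycle with at least 75% dosing, the patient is evaluable and counts as having no DLT.

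**Illustration of size.** The protocol states no DLT rate, power or error rate, so there is no figure to reproduce. Both inputs below are assumptions: the true DLT rate p, and the share f of DLTs that the literal wording misses.

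A dose level passes with 0 of 3 DLTs, or with 1 of 3 followed by 0 of the next 3 (expansion to exactly six). With q the counted rate:

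P(pass) = (1−q)³ + 3q(1−q)⁵

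- Missed event counted as no DLT: q = p(1−f).
- Patient replaced: q = p(1−f)/(1−pf).

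For p = 0.30 and f = 0: 0.343 + 0.9 × 0.168 = 0.494.

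| f (p = 0.30) | q, counted as no DLT | P(pass) | q, replaced | P(pass) |
|---|---|---|---|---|
| 0 | 0.300 | 0.494 | 0.300 | 0.494 |
| 0.10 | 0.270 | 0.557 | 0.278 | 0.539 |
| 0.25 | 0.225 | 0.654 | 0.243 | 0.614 |
| 0.50 | 0.150 | 0.814 | 0.176 | 0.759 |

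With a quarter missed, the pass probability at other true rates moves from 0.709 to 0.798–0.814 (p = 0.2), from 0.309 to 0.428–0.494 (p = 0.4), and from 0.172 to 0.265–0.351 (p = 0.5). The formula fits the three-to-six-patient continuous cohorts. It does not describe the intermittent cohorts of 12 or 4–12 patients in Table 3.

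**Attribution of laboratory DLTs.** Section 4.1.2 requires drug-relatedness, and Section 4.1.1 requires the event to be considered related to the combination. Section 5.10.3 collects causality on AEs. It keeps a mandated laboratory deterioration out of AE reporting unless it meets a seriousness criterion or is the reason for discontinuation; if signs or symptoms accompany it, the sign or symptom is the AE. An asymptomatic, non-serious Grade 4 platelet count after which treatment continues is therefore a named DLT with no stated field for its causality. The same holds for an asymptomatic Grade 3 result in mandated chemistry, which would fall under the fifth DLT item.

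**The case against.** The best defence is that nobody would apply the text literally. The other sections make Grade 3 look like a slip for Grade 3 or higher. Section 4.1.1 bases escalation on all available data, and Section 7.6 gives the decision to a committee with at least three physicians, who are unlikely to regard a related Grade 4 or fatal event as less than dose-limiting. Grade 4 haematological toxicity is listed by name, and some severe non-haematological events would be caught by the delay item. All of this stands and lowers the practical risk. It does not repair a rule that reaches the right answer only if it is overridden.

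On the laboratory side, a reader might infer that asymptomatic marrow toxicity goes unrecorded or lies outside the primary endpoint. The protocol does not support that:

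- Blood counts and chemistry are taken weekly (Table 4, footnote g). Clinically significant abnormal values go on the CRF (Section 5.6.1), and laboratory results are summarised in the study report (Section 5.10.3).
- Section 7.4.2 makes haematology and clinical chemistry variables of the primary objective, and bases the MTD on the safety data as a whole.
- Section 4.1.2 names the marrow DLTs without requiring an AE report.
- Under Section 4.5.3.1 a patient whose counts have not recovered after a hold of more than 14 days should be removed from the study. The count is then the reason for discontinuation and so an AE with a causality rating.
- Grade 3 thrombocytopenia is not a DLT, so not reporting it as an AE cannot lower the DLT count.
- Section 5.10.2 and Appendix B give blood dyscrasias as examples of serious events, a further route to AE status.

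A reader might also infer that the commonest DLTs are the ones missed. The protocol gives toxicity rates, such as myelosuppression in 25% to 30% of patients on cisplatin (Section 2), but no DLT frequencies, so nothing can be said about which DLTs are commonest.

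**Conclusion.** The point holds for non-haematological events. As written, Section 4.1.2 leaves related Grade 4 and Grade 5 non-haematological toxicity off the DLT list unless another item applies. With Sections 4.1.1 and 4.1.3, the affected patient can become unevaluable and replaceable. The events stay in the toxicity evaluation; what they can leave is the count that drives expansion and the MTD.

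The documents do not fix the size. The rise from 49% to between 61% and 65% rests on an assumed 30% DLT rate, an assumed one-quarter miss share and literal application of the text. Because the wording appears to be a slip and the committee reviews all the data, the real effect is probably smaller. The correction is still worth making, because it is cheap and concerns the trial's main decision rule.

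The laboratory point reduces to a gap in recording causality for asymptomatic, non-serious laboratory DLTs that do not end treatment. It does not show that the primary outcome is under-counted.

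**What to change.** 1. Reconcile Section 4.1.2 with Sections 4.1.1, 4.1.3, 4.4.6.1, 4.5.3.6 and 4.5.3.8 (including Table 8), so that the DLT definition states expressly how Grade 4 and Grade 5 non-haematological events count. The sponsor should confirm whether Grade 3 or higher was meant. This is one wording change.
2. In Section 5.10.3, require grade and causality for each drug to be recorded for any laboratory event that meets a DLT criterion, whether or not it is otherwise reportable as an AE. This takes one sentence and CRF completion guidance, and adds a few recorded AEs.

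Neither change affects the sample size or the visit schedule.
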